### **Safety of magnesium supplementation**

Adverse effects of magnesium caused by ingestion of food hadn't been identified since kidneys have mechanisms for the elimination of magnesium surplus. Nonetheless, adverse effects of magnesium secondary to the ingestion of supplements had been showed. The first symptoms of magnesium surplus are diarrhea and laxative effects that originates on the osmotic activity of non-absorbed salts in the intestine and colon, as well as gastric motility stimulation (these adverse effects are the reason why magnesium salts are used as laxative therapy). Magnesium salts that were reported for diarrhea are carbonate, chloride, gluconate and magnesium oxide.

Toxicity symptoms of magnesium surplus manifests when serum concentrations are above 4.2 mg/dL; and can include hypotension, nausea, vomit, facial blush, urine retention, ileus, depression and lethargy before it progresses to muscular weakness, dyspnea, extreme hypotension, irregular heart rhythm and cardiac arrest.

Individuals with renal impair are in major risks to present adverse effects secondary to magnesium supplementation. Symptoms of toxicity induced by magnesium had been observed in patients with renal impair that consumed moderate doses of magnesium laxatives or antacids.

Within clinical trials designed specifically to reduce incidence of hypomagnesemia induced by cisplatin using any magnesium salt it has been described the presence of vomit and diarrhea. However, one of the trials showed no gastrointestinal toxicity.

The Food and Nutrition Board of the US (FNB) established a maximum daily limit for magnesium supplementation in children: from 1 to 3 years, 65mg per day; from 4 to 8 years, 110 mg per day; and in children >9 years, 350 mg per day.

### **Interactions between magnesium supplements and drugs**

Various types of medicines have potential to interact with magnesium supplements or alter magnesium status. Medicines or supplements rich in magnesium can diminish the absorption of oral bisphosphonates, like alendronate (used for osteoporosis treatment). The administration between magnesium supplements and oral bisphosphonates must be separated by at least 2 hours.

Magnesium can form insoluble complexes with tetracyclines, like demeclocycline and doxycycline, as well as quinolones, like ciprofloxacin and levofloxacin. These antibiotics must be taken at least 2 hours before or 4 to 6 hours after a magnesium supplement.

Chronic treatment with loop diuretics (like furosemide and bumetanide), thiazide diuretics (like hydrochlorothiazide and ethacrynic acid), can augment the magnesium loss in urine. On the contrary, potassium-sparing diuretics (like amiloride and spironolactone) reduce magnesium excretion.

Inhibitors of proton-pump like esomeprazole and lansoprazole when taken for long periods (more than a year) can cause hypomagnesemia that originates with the impair of magnesium absorption in the intestine.

### **3. Problem statement**

Febrile Neutropenia (FN) is an important and serious health problem in children that receive chemotherapy because it increments the risk of major complications, it reduces the patient's quality of life, and increments treatment costs. Moreover, it is the most common diagnosis in children with cancer admitted into emergency rooms and the second cause of hospitalization, just after hospitalization for chemotherapy. In Mexico, FN incidence is 62% in children with solid tumors treated with cisplatin-based chemotherapy (CBC). Cisplatin is one of the most nephrotoxic drugs used in the clinic, this nephrotoxicity is showed by tubular damage that has electrolyte losses as a consequence, specially magnesium loss. Recently, an association between hypomagnesemia and the apparition of FN has been demonstrated. This finding can be explained based on the participation of magnesium as a cofactor in immune responses. Previous clinical trials, made in adult population, have showed that oral supplementation with magnesium in between chemotherapy cycles increment the serum concentration of magnesium and reduce hypomagnesemia episodes. With these evidences put together, we hypothesize that oral supplementation with magnesium oxide in between CBC cycles in children with solid tumors will maintain serum concentrations of magnesium in physiological parameters and in consequence this electrolyte will exercise its function in the immune system, contributing to the reduction of FN episodes. Therefore, the purpose of this protocol is to determine the efficacy of oral supplementation with magnesium to reduce incidence of febrile neutropenia in pediatric patients treated with cisplatin-based chemotherapy.

#### **4. Hypothesis**

Clinical evidence obtained in Mexican pediatric patients suggests that hypomagnesemia is associated to apparition of febrile neutropenia in patients that receive cisplatin-based chemotherapy. Previous clinical trials have reported that supplementation with magnesium salts reduce hypomagnesemia episodes in between 13 and 50%. With this in mind, we allow us to stablish the hypothesis that oral supplementation with magnesium oxide will reduce incidence of neutropenia febrile in 20% in pediatric patients treated with cisplatin-based chemotherapy.

#### **5. Objectives**

*General:*

- Determine the efficacy of oral supplementation with magnesium to reduce febrile neutropenia episodes in pediatric patients treated with cisplatin-based chemotherapy

*Specific:*

- Recruit patients for the clinical trial until completion of the sample size
- Monitor clinical accomplish of patients to magnesium supplementation
- Build and analyze the data base

*Secondary:*

- Determine if supplementation with magnesium oxide modifies the time of apparition of febrile neutropenia in pediatric patients treated with cisplatin-based chemotherapy
- Evaluate the safety of supplementation with magnesium oxide
- Determine the efficacy of oral supplementation with magnesium oxide to reduce incidence of hypomagnesemia in pediatric patients treated with cisplatin-based chemotherapy

## 6. Methodology

### *Study Design*

Randomized clinical trial, open-label, parallel groups.

### *Participants*

Pediatric patients with solid tumors that receive cisplatin-based chemotherapy.

### *Inclusion Criteria*

- Pediatric patients with solid tumors treated with cisplatin-based chemotherapy
- Both sexes
- Patients over 9 years old
- Informed consent signed by the parents
- Informed assent signed by the patient

### *Non-inclusion Criteria*

- Patients whose parents don't accept to participate
- Patients with magnesium loss tubulopathy diagnosed previous to CBC
- Patients with hypomagnesemia previous to CBC

### *Exclusion Criteria*

- Patients whose parents withdraw informed consent during trial

### *Procedure*

Basal status of trial will be integrated at the moment the attending physician indicates that the patient will be treated with cisplatin-based chemotherapy (CBC). The clinical monitor will establish contact with the parent of the patient and explain the purpose of the trial and will invite them to participate through signing the informed consent. Once the informed consent is signed the clinical monitor will explain the patient the purpose of the trial in order to obtain the informed assent.

To prove the hypothesis, it is required to randomize 107 CBC cycles to the intervention group and 107 CBC cycles to the control group. To determine whether the patient will receive supplementation or not in that CBC cycle, the clinical monitor will notify the principal investigator that a patient will commence treatment. In response the investigator will communicate the clinical monitor where to allocate the patient's CBC cycle. Randomize will be made by generating non-repeated random numbers with the program available at: <http://randomnumbregenerator.intemodino.com/es/generador-de-numeros-aleatorios.html>.

Patients assigned to the supplementation group will receive institutional care protocol plus a bottle with magnesium oxide tablets and will be explained that they should take a tablet daily. In the case that the patients were assigned to the control group they will receive institutional care protocol only.

Oral supplementation with magnesium consists on a daily tablet (245 mg magnesium oxide and 5mg magnesium gluconate, GNC, US). Supplementation will be interrupted when the patients returns for the administration of another cisplatin cycle or with the appearance of a febrile neutropenia episode. In the same sense, patients on control group will be monitored until an FN episode appears or until they return for the next cisplatin cycle.

The main outcome of this study is the apparition of febrile neutropenia that is defined as a neutrophils total count below  $1000/\text{mm}^3$  together with a unique temperature  $>38.3\text{ }^\circ\text{C}$  or a sustained temperature of  $\geq 38\text{ }^\circ\text{C}$  for over an hour. Patients with a neutrophils total count  $<100/\text{mm}^3$  will be considerate as a profound neutropenia. Clinical monitor will visit the emergency department every day to identify if one of the enrolled patients has been hospitalized due febrile neutropenia diagnosis.

To evaluate if oral supplementation with magnesium reduces secondary to CBC hypomagnesemia's, serum magnesium will be quantified before CBC and it will be measured again after the apparition of febrile neutropenia or at the moment the patients returns to another CBC cycle. Serum concentrations of magnesium below  $1.6\text{ mg/dL}$  will be considered as hypomagnesemia.

Daily maximum intake of magnesium supplements recommended for children over 9 years is  $350\text{ mg}$ . Nevertheless, the dose that will be used on this protocol is less that the recommended, it is necessary to evaluate safety of supplementation with magnesium in pediatric patients with cancer. To fulfill this purpose, each patient will be given a binnacle where they will register adverse effects that could be presented, such as diarrhea, nausea, vomit, etc.; binnacle is showed in Appendix 1. Moreover, clinical studies like hematic biometry, and other biochemical tests will be performed to determine if there is hepatotoxicity (ALT, AST and alkaline phosphatase), nephrotoxicity (creatinine) and cardiotoxicity (LDH). Biochemical determination will be made on both groups at the basal status and before every CBC cycle. Oral supplementation with magnesium will be interrupted in patients that present severe adverse reactions. All adverse reactions will be registered according NOM-220-SSA1-2015.

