## Magnesium

Magnesium is the fourth most abundant cation in organisms and has a role as a cofactor of 300 enzymatic systems, especially in reactions where ATP (adenosine triphosphate) intervenes, since it stabilizes negative charges of triphosphates. Magnesium is necessary for generation of energy in glycolysis, it forms part of the ATP-Mg complex, and is an important enzymatic cofactor. In mitochondria, enzymes use ATP and ADP-magnesium chelate as substrates for phosphate transference.

Magnesium's presence is important to maintain an adequate supply of necessary nucleotides for the synthesis of DNA and RNA that produces in cellular proliferation. Likewise, cellular replication needs protein synthesis, that diminishes with the depletion of magnesium supply.

Magnesium is most abundant in the bones (50-60%) and in minor proportion in muscles. Just 1-2% is found in extracellular liquid, and the rest is localized in the inside of cells, where is the second most abundant cation, after Potassium. Magnesium corporal deficiency appears with concentrations minor to 1 mg/dL. Approximately, 25% of serum magnesium is bonded to proteins, most to albumin; 15% forming other complexes; and 60% is free; the ionized form of magnesium is the one with physiological activity.

With an average diet people ingests about 300 mg/day of elemental magnesium. Near 30-40% of ingested magnesium is absorbed long in the gastrointestinal tract, mainly in the jejunum and ileum. Before a deficient magnesium ingest on the diet, non-saturable passive mechanisms of absorption and saturable active transport increase intestinal absorption around 70-80%.

Kidney is the main organ involved in magnesium homeostasis. Renal management of magnesium is a filtration-reabsorption process. No description of tubular secretion of

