## 7. Analysis data plan

Continuous variables with normal distribution will present as means and standard deviation. If variable have free distribution they will be presented as median and interquartile ranges. Categorical variables will be presented as frequencies and percentages. Operability of variables is showed at Appendix 3. Statistic differences at basal status will be calculated through t-Student test for continuous variables, whilst qualitative variables will be contrasted by  $\chi^2$  test. A  $p < 0.05$  will be considered as statistical significance.

Proportion of patients with febrile neutropenia will be calculated in both groups means the division of number of cases with febrile neutropenia between the total of CBC cycles assigned to each group (experimental or control). Efficacy of supplementation with magnesium will be determined through calculation of Relative Risks with Confidence Interval of 95% (CI 95%). Relative Risks will be considered significant when the value of CI95% don't cross the unit. Furthermore, Absolute Risk Reduction and Number Needed to Treat will be calculated. To adjust principal confounding variables, a Multivariate Analysis will be made with a Multiple Logistic Regression. Analysis by protocol (just patients that finish protocol) and by intention to treat (including all patients) will be made. Statistical analysis will be made performed with SPSS software v.21 (Chicago, IL, US).

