### *Sample Size Calculation*

Necessary number of patients was estimated considering a normal distribution means two proportions formula, using  $\alpha = 0.05$  (two tails),  $\beta = 0.20$ , 1 on 1 proportion of assignment to each group. For calculus it was considered that non-exposed group will have a proportion of 62%, while supplemented group will have a proportion of 42% (delta

20%). With the previous conditions and considering a continuity correction, to perform the study it is required to randomize 214 cycles and assign 107 to control group and 107 to supplemented group. Calculus was done with Sample Size Calculator for Designing Clinical Research by University of California San Francisco, available at <http://www.sample-size.net/sample-size-proportions/>.

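### If the CBC cycle is the unit of randomisation, possible carry-over into control cycles is neither prevented, recorded nor analysed; the unit itself must first be settled

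*Combined protocol and SAP*

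**What the plan says.** **Unit of allocation.** Under Procedure, the investigator's answer is needed "To determine whether the patient will receive supplementation or not in that CBC cycle", and what is allocated is the patient's cycle. The sample size is 107 cycles per arm, with "1 on 1 proportion of assignment to each group". Section 7 divides FN cases by "the total of CBC cycles assigned to each group (experimental or control"). The Abstract (Materials and Methods), however, has children randomised when CBC is indicated, and Study Design reads "Randomized clinical trial, open-label, parallel groups". No section says how many cycles a child may contribute, or whether a child keeps the same arm.

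**End of supplementation.** Under Procedure, "Supplementation will be interrupted when the patients returns for the administration of another cisplatin cycle", or when an FN episode appears. The same section also interrupts it for severe adverse reactions.

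**Tablets.** The supplemented group receives "a bottle with magnesium oxide tablets" and takes one tablet daily. No return or count is described. Section 5 lists adherence monitoring as an objective but gives no method.

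**Data and analysis.** The capture sheet (Appendix 2) records the folio, CBC start date, number of cycles received, previous FN and hypomagnesemia, and magnesium before and after supplementation. Neither it nor the variable list (Appendix 3) has a field for the current or previous arm. Section 7 has no term for previous arm or for repeated cycles within a child.

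**The concern.** If allocation is by cycle, the trial is in effect an unplanned crossover. A control cycle can come straight after a supplemented one, and there are two ways it could be affected.

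1. **Physiological carry-over.** When no FN or severe reaction has occurred, supplementation has continued up to the start of the next cycle. The child may then begin a control cycle with the magnesium status that the trial hopes to improve.
2. **Leftover tablets.** When FN stops supplementation early, tablets may remain at home. The trial is open-label and nobody is asked to collect them.

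Either could lower FN and hypomagnesemia in part of the control arm. The relative risk, absolute risk reduction and number needed to treat would then be pulled towards no effect, for the main objective and for the hypomagnesemia objective. The plan has no analysis that would show this. Tablet use that is not recorded at the time cannot be recovered later.

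**Working it through.** **The plan's own figure.** The inputs are in Sample Size Calculation: the "non-exposed group will have a proportion of 62" per cent, the supplemented group 42%, two-sided α = 0.05, β = 0.20, 1:1, with continuity correction. The two-proportion formula gives 97 per arm uncorrected and **107 corrected**, which matches the plan. At 107 per arm, power for 62% against 42% is 83.8% by the uncorrected formula (80.2% corrected). The calculation assumes independent cycles and no carry-over.

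**Share of control cycles at risk.** Let each child contribute *m* cycles, each allocated 1:1 independently. The documents do not give *m*. Of the *m* cycles, *m* − 1 have a predecessor, and half of those predecessors are supplemented, so

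f = (m − 1)/(2m), which is 25% for m = 2, 37.5% for m = 4 and 41.7% for m = 6.

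The same share applies to supplemented cycles, because the previous allocation is independent of the current one. The form of the carry-over therefore decides whether there is any bias.

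**Form A: carry-over adds equally in both arms.** Let a fraction *c* of the 20-point effect carry over (also assumed). With m = 4 and c = 0.5, both arms fall by 0.375 × 0.5 × 0.20 = 0.0375.
- Control: 62% − 3.75 = 58.25%. Supplemented: 42% − 3.75 = 38.25%.
- Difference: 20.0 points, unchanged. RR moves from 0.42/0.62 = 0.68 to 0.3825/0.5825 = 0.66, so it is not diluted.

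**Form B: saturating carry-over, in which supplemented cycles gain nothing more.** Control risk = 0.62 − 0.20·f·c, and supplemented risk stays at 0.42. Use of leftover tablets in control cycles works in the same direction.

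| m | c | Difference (points) | RR | NNT | Power at 107 per arm (uncorrected) | Cycles per arm for 80% (corrected) |
|---|---|---|---|---|---|---|
| any | 0 | 20.0 | 0.68 | 5.0 | 83.8% | 107 |
| 2 | 0.25 | 18.8 | 0.69 | 5.3 | 78.8% | 121 |
| 4 | 0.25 | 18.1 | 0.70 | 5.5 | 75.9% | 130 |
| 4 | 0.5 | 16.3 | 0.72 | 6.2 | 66.4% | 160 |
| 4 | 1 | 12.5 | 0.77 | 8.0 | 44.8% | 266 |
| 6 | 1 | 11.7 | 0.78 | 8.6 | 40.0% | 304 |

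Only the directly preceding cycle is counted.

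**Allowing for the FN stop.** At the planned 42% FN rate, 58% of supplemented cycles run on to the next cycle. If only those carry over, m = 4 and c = 0.5 give 0.20 × 0.375 × 0.5 × 0.58 = 0.022. The difference is then 17.8 points.

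**What an analysis could recover (m = 4).**
- Cycles not preceded by a supplemented one: 107 × 0.625 ≈ 67 per arm, with about 64% power for 62% against 42%.
- First cycles only: 107/4 ≈ 27 per arm, with about 31% power.
- A main effect of previous arm does not correct Form B. With c = 0.5 the arm difference is 20 points after a non-supplemented cycle and 10 after a supplemented one. Previous arm is balanced between arms, so adjusting for it still averages the two: 0.625 × 20 + 0.375 × 10 = 16.3. A current-by-previous-arm term is needed to see the contrast.

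**The case against.** **The premise may not hold.** No section says that a child is re-randomised at each cycle, and the Abstract and Study Design can be read as one allocation per child. If that is meant, f = 0 and the problem disappears. This stands, and it is why the unit comes first in the fix.

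**Dilution is not shown.** A reader might infer that control cycles do carry magnesium over and that the effect is diluted. The documents do not support that. They give no duration of effect, no number of cycles per child and no evidence that tablets are left over or used. The Background statement "Magnesium is most abundant in the bones (50-60"%) describes body distribution. It does not show that a daily tablet fills stores that protect a later cycle. The Background also says that the kidneys eliminate surplus magnesium and that cisplatin damages its reabsorption, and the next control cycle brings new cisplatin. Hypomagnesemia before CBC bars inclusion; if this is reapplied at each cycle, which the text leaves open, it would limit serum differences at the start. Form A also shows that even real carry-over need not bias the difference.

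**Supplementation does not always run to the next cycle.** FN and severe adverse reactions end it sooner, so there is often a gap. This stands and shrinks the illustration to 17.8 points. It also creates the situation in which tablets may be left over.

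**The previous arm might be recoverable.** A reader might also infer that no later analysis could detect carry-over. That is too strong. Intention-to-treat analysis requires allocation to be held somewhere, and folio, dates and cycle counts could be linked to such a list. Magnesium before the cycle gives a partial check. But no retained list is described, and tablet use could not be rebuilt from one.

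**Conclusion.** A cheap improvement, not a demonstrated bias. What holds is that the sections disagree on the unit of randomisation. If the unit is the cycle, the plan does not collect tablets, record the previous arm or analyse carry-over. Dilution then requires either leftover tablets taken in control cycles or a carry-over that helps control cycles more than supplemented ones.

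The size cannot be fixed from the documents. Under the saturating form, with assumed values of 2 to 6 cycles per child and 25% to 100% carry-over, the 20-point difference falls to between 18.8 and 11.7 points. The middle case (4 cycles, half carry-over) is 16.3, or 17.8 if only FN-free cycles carry over. Zero dilution is equally compatible with the text. The 107 per arm is correct arithmetic for its stated inputs.

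**What to change.** 1. State whether the child or the cycle is randomised, and make the Abstract, Study Design and Procedure agree. If each child is allocated once for all cycles, items 2, 3 and 5 are not needed for carry-over, but repeated cycles within a child still have to be handled.
2. If the cycle is the unit, have the clinical monitor collect the bottle and count the remaining tablets when the child returns for the next cycle or is admitted with FN.
3. Add current arm, arm of the previous trial cycle (none, control, supplemented) and trial cycle number to Appendices 2 and 3.
4. In Section 7, keep the all-cycle comparison as the fixed primary analysis. Include the pre-cycle magnesium already measured in the adjusted model, and account for repeated cycles within a child.
5. Pre-specify three sensitivity analyses: the comparison in cycles not preceded by a supplemented one, the first-cycle comparison, and a current-arm by previous-arm term. Do not let the efficacy conclusion move to the first-cycle estimate when results differ. Such a rule depends on the data and, at 4 cycles per child, would rest on about 27 cycles per arm.

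**Cost.** A few capture-sheet fields, bottle collection at contacts that already take place, and extra analyses with wider intervals than the primary one. No additional patients.

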## Capture Sheet

“Efficacy of Oral Supplementation with Magnesium to Reduce Febrile Neutropenia in  
Pediatric Patients treated with Cisplatin-Based Chemotherapy: Clinical Trial”

Date \_\_\_\_\_

Folio 

E	M				
---	---	--	--	--	--

Date of birth (dd/mm/yy) \_\_\_\_\_ CBC start date (dd/mm/yy) \_\_\_\_\_

Gender (M/F) \_\_\_\_\_ Weight (kg) \_\_\_\_\_ Height (cm) \_\_\_\_\_ CS (m^2) \_\_\_\_\_

Diagnosis \_\_\_\_\_

Chemotherapy scheme \_\_\_\_\_

Number of chemotherapy cycles received \_\_\_\_\_

Other schemes received \_\_\_\_\_ Which one? \_\_\_\_\_

Previous febrile neutropenia episodes \_\_\_\_\_ How many? \_\_\_\_\_

Dates \_\_\_\_\_

Treatment \_\_\_\_\_

Previous hypomagnesemias \_\_\_\_\_ How many? \_\_\_\_\_

Dates \_\_\_\_\_

Treatment \_\_\_\_\_

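### Efficacy is decided on a crude relative risk although allocation is not described as stratified by chemotherapy scheme; a scheme-stratified relative risk would recover precision at almost no cost

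*Combined protocol and SAP*

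**What the plan says.** Allocation is described in Section 6, Procedure. The target is fixed: "it is required to randomize 107 CBC cycles to the intervention group and 107 CBC cycles to the control group". For each case, "the investigator will communicate the clinical monitor where to allocate the patient's CBC cycle". The sequence itself gets one sentence: "Randomize will be made by generating non-repeated random numbers with the program available at" a web address. Strata, blocks and minimisation are not mentioned there or elsewhere, and nothing explains how the numbers map to arms.

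Eligibility (Section 6) covers any solid tumour treated with cisplatin-based chemotherapy. Section 2 (Cancer treatment) names three tumour types treated with cisplatin at the hospital, and the capture sheet in Appendix 2 lists several companion drugs. That sheet also has a field for "Chemotherapy scheme". Appendix 3 defines diagnosis, accumulated drug doses and G-CSF use as variables, but not scheme.

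Section 7 takes FN cases over cycles assigned in each arm, forms the RR with a 95% interval, and calls it significant when the interval excludes 1. It then adds: "To adjust principal confounding variables, a Multivariate Analysis will be made with a Multiple Logistic Regression". No covariates are listed, and the model is given no role in the decision.

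**The concern.** The population mixes tumours and regimens, and the sponsor expects confounders, yet neither the described allocation nor the deciding estimate takes account of scheme. If FN risk differs by scheme and one arm happens to receive more cycles of the riskier one, the crude RR moves with that imbalance. The logistic regression does not settle this: it is open as to covariates, is on the odds scale, and comes second to the crude rule. If the two disagreed, the plan gives no way to choose between them. At stake are some power, and the credibility of a result obtained alongside a visible imbalance.

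**Working it through.** **Inputs from the documents.** FN risk 62% (control) and 42% (supplemented), two-sided alpha 0.05, power 80%, 1:1, continuity correction, 107 cycles per arm (Sample Size Calculation). The deciding rule is the crude RR with 95% CI (Section 7).

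**Assumptions, because the documents give no figures.** Half the cycles are on a higher-risk scheme. The gap in control FN risk between the two scheme classes is g = 0, 10, 20, 36 or 56 points, centred on 62% (g = 36 means 80% and 44%; g = 56 means 90% and 34%). Supplementation lowers risk by 20 points in each class. The 214 cycles are independent, with arm totals fixed at 107.

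**Step 1: the plan's own size.** n = [1.96·√(2·0.52·0.48) + 0.8416·√(0.62·0.38 + 0.42·0.58)]² / 0.20² = (1.385 + 0.583)² / 0.04 = 96.8. With continuity correction: (96.8/4)·[1 + √(1 + 4/(96.8·0.20))]² = 106.5, so 107 per arm. The stated size is reproduced, and nothing below changes it.

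**Step 2: how large a chance imbalance is likely.** The number of higher-risk cycles in one arm is hypergeometric (214 cycles, 107 higher-risk, 107 drawn). The between-arm difference in share has SD 6.9 points. P(10 points or more, either direction) = 0.171; P(14 or more) = 0.055; P(15 or more) = 0.028.

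**Step 3: what an imbalance does to the crude RR.** With no treatment effect and an imbalance d favouring magnesium, RR = (0.62 − g·d/2)/(0.62 + g·d/2).
- g = 0.20, d = 0.10: 0.61/0.63 = 0.968
- g = 0.40, d = 0.10: 0.60/0.64 = 0.938
- g = 0.36, d = 0.14: the risk difference shifts by 0.14 × 0.36 = 5.0 points, a quarter of the 20-point target

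At the planned RR of 0.42/0.62 = 0.677, the first case gives 0.677 × 0.968 = 0.656 or 0.677/0.968 = 0.700, depending on direction.

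**Step 4: crude against stratified.** The crude rule uses log RR with variance 1/a + 1/c − 2/107, where a and c are the FN counts by arm. The Mantel-Haenszel RR is Σ(a_k·n0_k/N_k) / Σ(c_k·n1_k/N_k) over scheme classes k, with the usual Greenland-Robins variance for its log. Simulation used 100,000 trials per row; Monte Carlo error on power is about 0.1 point.

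| Gap g (points) | Power: crude RR, unstratified allocation | Power: stratified RR, same allocation | Power: stratified RR, stratified allocation |
|---|---|---|---|
| 0 | 83.3% | 83.3% | 83.5% |
| 10 | 83.5% | 83.7% | 83.4% |
| 20 | 83.2% | 84.7% | 84.7% |
| 36 | 83.1% | 88.2% | 88.3% |
| 56 | 83.3% | 95.0% | 94.9% |

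If the effect is a constant ratio (0.677) rather than a constant 20 points, the gain is a little smaller: 83.3% to 84.1% at a 20-point gap and 83.7% to 87.9% at 40 points (15,000 trials each).

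**Step 5: type I error.** With no effect, the crude rule rejects in 4.5% to 4.7% of trials for every gap in the table. Among the roughly 8.6% of trials (half of 0.171) with an imbalance of 10 points or more favouring magnesium, the crude rule falsely claims benefit in 2.5%, 5.0%, 8.2% and 13.2% for gaps of 0, 20, 36 and 56 points, against a nominal 2.5%. The stratified RR stays between 2.0% and 2.6% in the same trials.

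**Step 6: unit of randomisation.** The Abstract randomises children; Section 6 randomises cycles. If each child contributes m cycles of one scheme to one arm, the SD in Step 2 is multiplied by √m. It becomes 9.7 points for m = 2 and 13.7 for m = 4 (both m assumed). P(10 points or more) is then about 30% or 47% by the normal approximation.

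**The case against.** The strongest reply is that randomisation already protects the test. Step 5 bears this out: chance imbalance is not bias, and the overall error rate holds whatever the gap. The shift from a typical imbalance is also small beside a planned RR of 0.677, and with a gap of 10 points or less nothing is gained. All of this stands, and it keeps the point minor.

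A second reply is that Section 7 already adjusts and the capture sheet already records scheme. That is only a partial answer, because the model's covariates are not named and it does not decide efficacy.

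Three stronger readings are tempting, and the documents do not support them.
- A reader might infer that allocation is unrestricted, from a single list. The fixed 107 and 107 totals are compatible with a rule that balances arm sizes, and the number of lists is not stated. Only the absence of any described stratification is supportable.
- A reader might take it as established that schemes differ in FN risk. This is plausible, but no section gives FN risk by tumour or scheme.
- A reader might conclude that the sequence must be rebuilt. The last two columns of Step 4 differ by no more than about the simulation error. At 80/44 the SD of the risk difference is 6.69 points for the crude estimate, 6.24 after adjustment alone, and 6.22 with stratified allocation. In an open-label trial in one department, where the investigator relays each allocation, small blocks within strata also make the next assignment easier to guess.

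**Conclusion.** The point holds as a minor improvement to the analysis. With no stratification described and a crude RR as the deciding estimate, an imbalance in scheme enters the efficacy decision unadjusted. The loss is in precision and in validity conditional on the imbalance that occurs; overall type I error is kept. The gain from a stratified RR runs from nothing (gap of 0 to 10 points) through about 1.5 points of power (20-point gap) to about 5 points (36) and 12 points (56). It rests on an assumed even split of schemes, assumed risk gaps and independent cycles. An even split is the least favourable: for a factor present in 30% of cycles, the chance of a 10-point imbalance falls from 17% to 10%. If children are the unit, imbalances would be larger, so the conflict between the Abstract and Section 6 matters here too.

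**What to change.** In Section 7, name as the analysis that decides efficacy a Mantel-Haenszel RR with 95% CI, stratified by two or three classes of chemotherapy scheme. Fix the classes before the first allocation, define them in Appendix 3, and assign each cycle from the scheme entered on the capture sheet before allocation. Report the crude RR alongside, and say that the logistic regression is supportive, with its covariates listed.

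Reconcile the Abstract and Section 6 on whether children or cycles are randomised. If children can contribute more than one cycle, state how the interval allows for that; the calculations above do not.

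Stratifying the allocation by the same classes is optional. If it is done, block sizes should vary at random and be kept from recruiting staff.

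The cost is a few sentences and one variable definition. The data are already collected, the sample size is unchanged, and if schemes turn out not to differ in FN risk, practically no power is lost.
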